Summaries of all efficacy endpoints will be performed for 12 months exposure. Where appropriate, 95% CIs around the mean change from Study Baseline or Period 2 Baseline (for Period 1 and Period 2 data, respectively) will be presented. (revised per Amendment 06)

No multiplicity adjustment is planned for the exploratory and PD endpoints. (revised per Amendment 03)

Pharmacokinetic Analysis

The Safety Analysis Set will be used for individual lemborexant and its metabolites M4, M9, and M10 plasma concentration listings. The PK Analysis Set will be used for summaries of lemborexant M4, M9, and M10, by dose, time, and day.

A population PK approach will be used to characterize the PK of lemborexant. For this approach, PK analysis data from this study will be pooled with relevant data from Phase 1 and 2 studies, and other Phase 3 studies if available. The effect of covariates (eg, demographics, concomitant medications) on the PK of lemborexant will be evaluated. The PK model will be parameterized for oral clearance (CL/F) and volumes of distribution. Derived exposure parameters such as area under the concentration-time curve (AUC) and maximum plasma concentration (C_{max}) of lemborexant and any other relevant parameters will be calculated from the model using the individual estimates parameterized for oral clearance and dosing history.

Pharmacokinetic/Pharmacodynamic Analyses

The PK/PD relationship between exposure to lemborexant and efficacy variables including but not limited to sSOL, sSE, and sWASO, and safety variables including but not limited to morning sleepiness and frequently occurring TEAEs, will be explored graphically. Any emergent PK/PD relationships will be evaluated by population PK/PD modeling. The population PK/PD analysis plan will be described and results will be reported in a separate document.

Population PK and PK/PD analyses will be performed using NONMEM Version 7.2 or later.

Safety Analyses

Evaluations of safety will be performed on the relevant Safety Analysis Set and On-Treatment Safety Analysis Set, as appropriate. The incidence of AEs, out-of-normal range laboratory safety test variables, abnormal ECG findings, out-of-range vital signs and weight, suicidality (eC-SSRS), and T-BWSQ (including frequency and percentage of subjects with T-BWSQ ≥ 3), along with change from Study Baseline in laboratory safety test variables, ECGs, and vital sign and weight measurements, will be summarized by treatment group and visit using descriptive statistics. This will be repeated for the 12-month LEM exposure (On-Treatment Safety Analysis Set), summarized by treatment group and duration of exposure. (revised per Amendment 06)

Customized MedDRA Queries (CMQ) for AEs that could potentially be considered cataplexy or seizure, somnolence, and related events, and preferred terms related to drug abuse liability, will be summarized. The results of the deliberation of the Adjudication Committee will be reported separately. (revised per Amendment 03)

Other Analyses

Secondary and exploratory endpoints may be additionally presented graphically or analyzed by modeling methods if warranted.

Interim Analysis (revised per Amendments 04 and 05)

No interim analysis is planned for this study.

Sample Size Rationale

The sample size was estimated for the comparison of LEM10 and LEM5 with PBO, with respect to the mean change from Study Baseline at the end of Month 6 of the mean sSOL, mean sSE, and mean

sWASO. This estimate was based on sequential gate-keeping procedure at the 0.05 α -level as described above. There is sufficient power for both the primary endpoint (sSOL) and key secondary endpoints (sSE and sWASO).

On the basis of the dose finding study E2006-G000-201 (Study 201) for the lemborexant total summaries at Days 8 to 15, the standard deviation of change from Study Baseline for sSOL is assumed to be 33 minutes, for sSE is assumed to be 12% and for sWASO is assumed to be 43 minutes. The LS mean treatment differences at Days 8 to 15 from Study 201 were as follows: for sSE 9.5% for LEM10 and 5.5%, for LEM5; for sWASO -26.6 minutes for LEM10 and -11.3 minutes for LEM5. As a result of the non-normal distribution of sSOL, the LS mean treatment difference is not available (geometric mean ratios were used). Therefore, estimating treatment difference using medians at Days 8 to 15 from Study 201, leads to a median treatment difference of approximately -6.8 minutes for LEM10. For LEM5, a median treatment difference is approximately -13.2 minutes.

To detect a treatment difference in sSOL of at least -8.7 minutes, a sample size of 300 per treatment group at 5% (2-sided) level of significance has >90% power for comparing a dose of lemborexant with PBO.

To detect a treatment difference in sSE of at least 5.5%, a sample size of 300 per treatment group at 5% (2-sided) level of significance has >99% power for comparing a dose of lemborexant with PBO.

For sWASO, total 900 subjects (300 per treatment group) will give 90% power to detect a difference of -11.4 minutes for LEM5 and LEM10 compared to PBO. The study is adequately powered to show the statistically significant difference from PBO for LEM10 as well as for LEM5.

The study also has adequate power for the secondary analysis of responders. A sleep onset responder is defined as follows: sSOL at Study Baseline is ≥ 30 minutes and mean sSOL at 6 months is ≤ 20 minutes, and a sleep maintenance responder is defined as follows: sWASO at Study Baseline is ≥ 60 minutes and mean sWASO at 6 months ≤ 60 minutes and shows a reduction of >10 minutes compared to Study Baseline. A total of 900 subjects gives >99% power to detect a treatment difference in sleep onset responder rates of 16% and sleep maintenance responder rates of 24.4%.

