The Follow-up Period will begin at the end of Period 2. Subjects will discontinue study drug but will continue to complete the Sleep Diary each morning until the EOS visit.

Premature Discontinuation of Study Drug

The subject may elect to discontinue the study at any time for any reason. Subjects who discontinue study drug prematurely at any time after randomization at Visit 3 (Study Baseline) will be encouraged to return to the site as soon as practicable (preferably within 7 days). These subjects will be encouraged to continue to complete all study assessments (excepting PK samples, which will not be taken), including the Sleep Diary, and to return for all subsequent clinic visits, without the administration of study medication.

Subjects who do not agree to this will undergo an Early Termination (ET) Visit and the EOS visit, as described in the Schedule of Procedures/Assessments. (revised per Amendment 01) Subjects who agree will undergo an Early Drug Discontinuation (EDD) Visit, during which all assessments will be conducted that would be made at an ET visit. These subjects need not attend the next regularly

scheduled visit if this falls within the visit window of the next visit. Subjects who discontinue early from study drug are considered on study as long as they return for their regularly scheduled visits.

Adjudication Committee (revised per Amendment 03)

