To assess rebound insomnia, both categorical analysis at the subject level and continuous analysis at the group mean level will be performed. For each of the first 3 nights and each of the 2 weeks of the Follow-up Period the proportion of subjects whose corresponding value for sSOL or sWASO exceeds the corresponding Screening Period value by 5 minutes will be summarized by treatment group and compared to placebo. The percentage of 'rebounders' between each treatment and placebo group will be analyzed using a Cochran-Mantel-Haenszel (CMH) test, adjusted for country and age group.

To assess statistical significance using the continuous data at the group mean level, the data will be analyzed using ANCOVA, adjusted for country, age group and treatment. The LS mean of each of the first 3 nights and each week of the Follow-up Period will be compared to the Screening Period between each treatment group and placebo. If the lower bound of the 95% CI of sSOL or sWASO for each of the first 3 nights and the mean of each week of the Follow-Up Period exceeds the upper

bound of a 95% CI for the values during the Screening Period in the given treatment group, it will be considered strong evidence for rebound insomnia. If the LS means for sSOL and sWASO for the Follow-up Period are all lower than for the Screening Period, then no rebound insomnia is suggested. Otherwise, the degree to which the parameters worsen, and the time point(s) at which they worsen will be considered to evaluate whether clinically meaningful rebound insomnia is present.

To evaluate morning sleepiness item on the Sleep Diary, the mean change from Study Baseline of the 1st 7 mornings after the 1st dose in Period 1, Month 1, Month 3 and Month 6 will be analyzed using MMRM, assuming MAR. Additionally, morning sleepiness change from both Study Baseline and Period 2 Baseline for the 1st 7 mornings after the 1st dose in Period 2, Month 9, and Month 12, and also the change from Screening of each of the 2 weeks of the Follow-Up Period will be summarized with mean and 95% CI's. (revised per Amendment 03)

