8.2 Secondary Objective(s)

The key secondary objectives of the study are:

- Determine the efficacy of LEM5 and LEM10 compared to PBO on subjective sleep efficiency (sSE) after 6 months of treatment in subjects with insomnia disorder
- Determine the efficacy of LEM5 and LEM10 compared to PBO on subjective wake after sleep onset (sWASO) after 6 months of treatment in subjects with insomnia disorder

Additional secondary objectives of the study are:

- Determine the efficacy of LEM5 and LEM10 compared to PBO on sSOL, sSE, sWASO, and subjective total sleep time (sTST):
 - over the 1st 7 nights of treatment
 - after 1 month of treatment
 - after 3 months of treatment
- Determine the efficacy of LEM5 and LEM10 compared to PBO on sTST at 6 months
- Evaluate the proportions of sleep onset and sleep maintenance responders to LEM5 and LEM10 compared to PBO as defined by response on sSOL or sWASO at 6 months and 12 months
- Evaluate the safety and tolerability of LEM5 and LEM10
- Evaluate the efficacy of LEM5 and LEM10 compared to PBO as measured by responses on the Insomnia Severity Index (ISI) and the Fatigue Severity Scale (FSS) after 6 months
- Evaluate rebound insomnia following discontinuation of treatment
- Evaluate morning sleepiness during and following completion of treatment
- Evaluate persistence of efficacy of LEM5 and LEM10 over 12 months

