9.5.3 Appropriateness of Measurements

Completion of sleep diaries by subjects is considered to be an appropriate method to measure changes in subjective sleep parameters, thereby allowing assessments of secondary efficacy in this study. The advantages of the electronic Sleep Diary to be used in this study include that the questions and instructional text have been adapted from sleep diaries that were developed by clinicians and researchers with expertise in insomnia disorder, and have undergone linguistic validation and cognitive debriefing to optimize their use in this study. The Sleep Diary will include questions to assess the subject's rating of sleep quality each night and sleepiness/alertness level in the morning.

The ISI has been widely used to evaluate the subjective impact of insomnia severity on psychosocial functioning, which is one type of daytime functioning impairment experienced by those with insomnia disorder. The FSS measures fatigue, which is another type of daytime impairment that is often a consequence of insomnia. This scale has been employed primarily in clinical trials of cognitive and behavioral treatments for insomnia disorder. Because the objectives of this study include assessing the response to lemborexant of both nighttime sleep and daytime impairment complaints, the ISI and the FSS will be evaluated for changes from baseline. The PGI-Insomnia, EQ-5D-3L and WPAI-GH will also be employed. These measures have been used in studies evaluating the impact of treatment for insomnia on patients' global perceptions of sleep quality and quality of life. Together these measures will provide a broad evaluation of the effects of lemborexant on each patient's sleep, daytime functioning, quality of life and productivity.

The safety assessments performed in this study, including clinical laboratory analyses, vital sign parameters, electrocardiograms, and assessment of AEs are standard evaluations to ensure subject safety. The C-SSRS, a standardized assessment required by regulatory authorities, will be used to evaluate any effects of lemborexant on suicidality. Additional safety-related assessments include evaluation of morning sleepiness and rebound insomnia, which will be measured using the validated Sleep Diary.

9.5.4 Reporting of Serious Adverse Events, Pregnancy, and Events Associated with Special Situations

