9.7.1.6 Efficacy Analyses

Where Sleep Diary endpoints are described, the time points refer to the mean of the final 7 nights before the visit unless otherwise stated.

Subjects who discontinue the treatment prematurely will be encouraged to continue to complete the assessments at the protocol defined times (retrieved drop out) until the scheduled time of termination. When available, these data will be used for efficacy analyses. If there are a substantial proportion of early withdrawals, a sensitivity analysis of the primary endpoint will be conducted.

Definitions of Baseline

For the analyses of PBO-controlled endpoints (ie, Day 1 to Month 6), “Study Baseline” is defined as the data captured during the Run-In Period (or during the Baseline Period). For the analyses of data that are not placebo-controlled (ie, Month 7 to Month 12), data from Month 6 visit will be used as the “Period 2 Baseline”. (revised per Amendment 06)

For other endpoints, baseline data are captured during the Run-In and Baseline Period. Details will be specified in the SAP.

12-Month Lemborexant Exposure

Twelve-month (12-month) lemborexant exposure summaries will be summarized by treatment (LEM5, LEM10) and duration of exposure (1 month [30 days] where appropriate, 3 months [90 days], 6 months [180 days], 9 months [270 days] and 12 months [365 days]). Treatment groups are LEM5 and LEM10, and include both (a) LEM Period 1 subjects on the

On-Treatment Full Analysis Set using the change from Study Baseline and (b) LEM Period 2 subjects previously receiving PBO on the On-Treatment Full Analysis Set using the change from Period 2 Baseline. (revised per Amendment 06)

Control of Type 1 Error

A sequential gate-keeping procedure including sSOL (primary endpoint), sSE and sWASO (key secondary endpoints) at Month 6 will control for type 1 error. In order to move from 1 step to the next (steps a to f; below) the outcome must be significant at 0.05 (2-sided).

- a. Change from Study Baseline at Month 6 in sSOL, LEM10 compared to PBO
- b. Change from Study Baseline at Month 6 in sSOL, LEM5 compared to PBO
- c. Change from Study Baseline at Month 6 in sSE, LEM10 compared to PBO
- d. Change from Study Baseline at Month 6 in sSE, LEM5 compared to PBO
- e. Change from Study Baseline at Month 6 in sWASO, LEM10 compared to PBO
- f. Change from Study Baseline at Month 6 in sWASO, LEM5 compared to PBO

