3.4 Efficacy Analyses

Efficacy analyses for Treatment Period 1 will be performed on the FAS unless otherwise specified. Different baseline values will be used for endpoints defined during Treatment Period 1 (ie, Day 1 to Month 6) and during Treatment Period 2 (ie Month 7 to Month 12). Baseline values for each efficacy parameter are specified in [Section 6.1.1](#). The On-Treatment FAS will be used for the on treatment summaries produced by time on treatment.

Unless specified otherwise, all efficacy endpoints will be derived by calculating the average of weekly (7 days) diary parameter values ([Section 6.1](#)).

12-month LEM exposure data will be summarized by treatment (LEM5, LEM10) and duration of exposure (1 month [30 days], 3 months [90 days], 6 months [180 days], 9 months [270 days] and 12 months [365 days]). Treatment groups are LEM5 and LEM10, and include both (a) LEM Period 1 subjects on the On-Treatment Full Analysis Set using the change from Study Baseline and (b) LEM Period 2 subjects previously receiving PBO on the On-Treatment Full Analysis Set using the change from Period 2 Baseline. No hypothesis test will be performed for efficacy endpoints beyond the Month 6 visit.

The primary and key secondary endpoints comparisons are tested following the gate-keeping testing procedure described in [Section 3.3.3](#) to control for the overall type I error at the 0.05 significance level. The first primary efficacy endpoint comparison will be performed at the 0.05 significance level. The subsequent testings will only proceed if the previous test is statistically significant at the 0.05 level.

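### The Period 1 placebo comparison of morning sleepiness keeps diary mornings recorded after study drug was stopped, so beyond week 1 it does not measure sleepiness during treatment.

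*Protocol*

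**What the plan says.** Protocol section 8.2 sets the objective: "Evaluate morning sleepiness during and following completion of treatment". Section 9.5.3 places the item with safety: "Additional safety-related assessments include evaluation of morning sleepiness and rebound insomnia". The PK/PD text in the synopsis refers to "safety variables including but not limited to morning sleepiness and frequently occurring TEAEs".

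The placebo comparison, however, is placed among the secondary efficacy analyses (synopsis and protocol 9.7.1.6.2): "Month 1, Month 3 and Month 6 will be analyzed using MMRM, assuming MAR". SAP 3.4.2.4 lists the item under the diary efficacy measures and adds Months 2, 4 and 5. It uses MMRM under MAR without imputation.

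On subjects who stop drug, the synopsis says: "These subjects will be encouraged to continue to complete all study assessments (excepting PK samples, which will not be taken), including the Sleep Diary", and that this continues "without the administration of study medication". Protocol 9.7.1.6 says of such retrieved-dropout data: "When available, these data will be used for efficacy analyses". SAP 3.4 adds: "Efficacy analyses for Treatment Period 1 will be performed on the FAS unless otherwise specified". SAP 6.1.2 and Table 9 take the 7 mornings in a study-day window, whether or not a dose was taken the night before.

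**The concern.** Once the drug has cleared, a morning with no dose the night before carries no residual drug effect. Under the planned rules such mornings still count in the randomized lemborexant arm at Months 1 to 6. The reported contrast then mixes subjects on drug with subjects who have stopped, and it need not equal the difference between lemborexant and placebo while the drug is being taken.

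The study rationale (protocol 7.2) includes showing doses without meaningful morning sleepiness. If the on-drug effect is a worsening, a diluted difference looks better than it should. The 8.2 objective also separates sleepiness during treatment from sleepiness afterwards, and the second part has its own Follow-up endpoints. Off-drug mornings in the Period 1 means blur that separation.

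**Working it through.** **Is anything exempt?** SAP Table 4 names estimands for the primary endpoint only. Its MMRM-under-MAR row counts data after dropout as included. No text exempts morning sleepiness. The per-protocol, completer and tipping-point analyses are specified only for the primary and key secondary endpoints.

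**The plan's own figure.** Protocol 9.7.2 considers 50% discontinuation at Month 6: 300 × (1 − 0.50) = 150 remaining per group, as stated. This is a pessimistic scenario used to justify safety exposure. No effect size, SD, stopping rate or retrieved-diary rate is given for morning sleepiness.

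**Dilution.** Let d be the share of a lemborexant arm that has stopped drug and r the share of stoppers still completing the diary. Both are assumed, except d = 50%, which is the plan's worst case. The off-drug share of observed diaries is

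f = d·r / (1 − d + d·r).

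If off-drug mornings carry no drug effect, the estimate is (1 − f) times the on-drug difference. For d = 0.20 and r = 0.5: f = 0.10 / (0.80 + 0.10) = 0.111, so the estimate is 0.89 of the on-drug difference.

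| Stopped, d | r = 0 | r = 0.25 | r = 0.5 | r = 1 |
|---|---|---|---|---|
| 10% | 1.00 | 0.97 | 0.95 | 0.90 |
| 20% | 1.00 | 0.94 | 0.89 | 0.80 |
| 30% | 1.00 | 0.90 | 0.82 | 0.70 |
| 50% | 1.00 | 0.80 | 0.67 | 0.50 |

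**Simulation check.** The set-up was 4 visits, correlation 0.6, an on-drug effect of 0.3 SD, sleepier subjects more likely to stop at the same rate in both arms, and maximum likelihood under MAR.

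- About 22% stopped, off-drug mornings kept: 0.94, 0.89 and 0.78 of the true on-drug effect for r = 0.25, 0.5 and 1.
- About 51% stopped, off-drug mornings kept: 0.79, 0.67 and 0.49.
- Off-drug mornings set to missing at drug stop: 0.99 to 1.01 in every case.

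The last result shows that the filter removes the dilution. It does not test MAR, because stopping in the simulation depended only on ratings already observed.

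**The case against.** Four points on the other side have weight.

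**The planned estimate is valid for a treatment-policy question.** A reader might infer that it is simply biased toward no effect. The documents do not support that, because no estimand is named for this endpoint. What stands is narrower: the planned estimate does not answer the during-treatment objective.

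**The direction is not fixed.** The item asks how sleepy or alert the subject feels, from 1 (extremely poor) to 9 (extremely good). Better sleep could raise it as residual drug lowers it. If the net effect is a benefit, off-drug mornings dilute the benefit. Protocol 7.1.2.2.2 also reports that next-day sleepiness in Study 201 did not differ from placebo at doses up to 10 mg. A reader might infer that the analysis leans toward a safety claim, but that holds only if the on-drug effect is a net worsening.

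**The size may be small.** Continuing the diary off drug is only encouraged. Protocol 9.4.7.2 also requires subjects who have stopped drug to leave the study if they start a new insomnia treatment, which lowers r. A reader might reach a larger loss by supposing that stoppers had three times the effect of stayers. With 20% stopped and all retrieved, that sets 0.8 against 0.8 × 1 + 0.2 × 3 = 1.4. Most of that gap is selective stopping: those still on drug show 1.0, so the retained off-drug mornings cost 0.8 against 1.0, or 20%. The documents give no basis for the three-fold ratio.

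**Other on-drug information is planned.** The first-7-mornings comparison against placebo is nearly all on drug. Somnolence events are summarized by arm, including placebo, in Period 1. Morning sleepiness is summarized by duration of lemborexant exposure. These narrow the gap, but the exposure summaries have no placebo column and event counts are not the diary rating.

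**Conclusion.** The point holds in a limited form. From Month 1 to Month 6 the plan has no placebo-controlled comparison of morning sleepiness confined to on-drug mornings, although its objective asks about sleepiness during treatment. Under the assumed rates, dilution of any on-drug difference is about 3% to 20% for 10% to 20% stopped. The 50% figure is an upper bound that needs both the plan's worst-case stopping and complete diary retention.

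These sizes rest on off-drug mornings carrying about no drug effect. The absence of rebound insomnia in Study 201 is consistent with this but concerns sleep, so it does not establish it for morning alertness. No confirmatory test or multiplicity control depends on this endpoint, so this is a low-cost improvement in interpretation and not a threat to the trial's main conclusions.

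**What to change.** In SAP 3.4.2.4, with matching text in protocol 9.7.1.6.2, keep the planned MMRM and add a second pre-specified one beside it. The second should:

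- compare LEM5 and LEM10 with placebo on morning sleepiness, with the same covariates and visits;
- use only diary mornings up to the day after the last dose of study drug, in all three arms;
- treat later mornings as missing under MAR, and apply the existing rule of at least 4 of 7 values to the mornings that remain.

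State that conclusions about sleepiness during treatment rest on this second analysis, and that the planned one answers the treatment-policy question. A by-arm summary of the last 7 on-treatment mornings is optional and descriptive, since it mixes different treatment durations.

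The cost is a paragraph of SAP text, a date filter and one table. The last-dose date is already collected (protocol 9.3.3), and SAP section 1 allows documented changes before unblinding. The downside is that the added analysis is conditional on staying on drug and relies on MAR after drug stop, which is why it should stand beside the planned comparison and not replace it.
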